1.0 STUDY OBJECTIVE

The primary objective of this clinical study is to prove that a user aided with ClearRead CT InSight is *superior to the unaided reader for detecting actionable lung nodules*.

The secondary objective of this clinical study is to prove that the reader's reading time is not significantly increased when aided with ClearRead CT Insight.

2.0 STUDY ENDPOINTS

1. The scores, likelihood of cancer, along with clinical actions at specific cut-points given by the radiologists with and without ClearRead CT Insight and compared to the true status of the study-case. The frequency of the scores for each method (Unaided and aided with CLEARREAD CT INSIGHT) will be recorded. This information will be used to construct a localized receiver operating characteristic (LROC) curves. Cut points will be used to establish point based estimates, namely; Sensitivity, Specificity, PPV and NPV.
2. Reading times associated with unaided and aided reads will also be assessed.
3. Machine performance will be measured as free response operating curve (FROC) or nodule sensitivity versus patient false positive rate

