3.0 STUDY DESIGN

3.1 OVERVIEW

A reader study with at least ten (10) participating radiologists will be conducted. A localized receiver operating characteristic curve will be used to evaluate radiologists' diagnostic performance (in terms of the trade-off between the sensitivity and specificity when the decision criteria changes) in the detection of lung nodules on lung CTs with and without the

usage of the *ClearRead CT Insight* system. The time needed for the review and interpretation of each case will also be recorded.

An initial (baseline) interpretation will be made by each of the radiologists based on the Lung CT in its original form. At a minimum of one month later, each radiologists will again interpret the same images viewing the pair of CRCTI CT series: Two sets of CT images (standard with CADe marks and processed with vessel suppression) will be presented on either one large monitor or two adjacent monitors.

During the baseline reading the radiologist will mark the location of the actionable nodules and assign a score. The radiologist will also indicate the recommended method of follow-up (Contrast CT, PET-CT, CT Follow-up, Biopsy).

During the second reading session (concurrent read), the radiologist will be presented with a standard appearing CT with CADe marks placed (left image) and the vessel suppressed same slice with the vessel suppressed view (right image). The second image, vessel suppressed, will be grayed out until the radiologist move the mouse to the second panel. The radiologist will mark locations. These may or may not correspond to the locations of the CAD markers. As before, the radiologist will assign a level of suspicious to each mark and indicate the need, if any, of an additional diagnostic action (Contrast CT, PET-CT, CT Follow-up, or Biopsy).

[figure not shown]
Based on the levels of suspicion for each nodule and the associated likelihood ratings, LROC curves will be constructed for both the baseline and the concurrent reads and the significance of any difference will be calculated. The recommendations for further action (Contrast CT, PET-CT, CT Follow-up, or Biopsy) will be used to calculate sensitivity and specificity, PPV and NPV.

Number and types of cases:

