Retrospective lung CT image series from approximately 300 patients will be included in the study. Approximately one hundred (100) of the patients will have pathology confirmed cancers and approximately two hundred (200) of the patients will be CTs associated with normal patients. Also included as nodule images are those where the actionable nodule was not acted on at that time, but was detected and acted on based on a subsequent CT. These are the prior images where the nodule can be identified and its location is the same as on the “current” image confirmed by the radiologist expert panel (using a majority of three as the decision criterion).

The selected sample, randomly selected from a larger pool of CT cases will be enriched in the following way:

1. Lung nodules (cancers in this study) will be tumor size T1a (20 mm or less). The proportion of nodules 20 mm or less may be increased since this is where we expect the major impact of this software to be.
2. Non-Solid (ground glass) nodules will be added to the sample (based on availability) to determine the performance of the system on non-solid nodules. For this group, to have sufficient cases, we may have to include benign (non-malignant) non-solid nodules.
3. In this project, VIRGINIA TECH will perform a Machine Test of the ClearRead-CT-Insight algorithm followed by a reader performance evaluation study. Riverain will provide a system configured with the operating point set to be used for the reader studies and a configuration for an “open” system to be used for machine testing and FROC generation. Figure 1 shows the reader performance study consists of two arms; **Arm 1**: a baseline read (no secondary content) and **Arm 2**: concurrent, CAD augmented read.

1/12/2015

Riverain Technologies, LLC - Confidential

Figure 1: ClearRead Insight Reader Study Design

1st Arm: Do baseline (measure time, readers score regions according to action and suspiciousness) – mark all locations of concern

2nd Arm: Concurrent read (measure time, readers score regions according to action and suspiciousness) – mark all locations of concern

The primary study hypothesis is that the adjunctive use of ClearRead CT Insight is superior to use of standard lung CT images alone, as measured by the area under the LROC curve.

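### PPV and NPV will come from a case set enriched to about one-third cancer, with no prevalence adjustment or caveat, so their levels and absolute differences are specific to the study mix

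*Combined protocol and SAP*

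**What the plan says.** Section 2.0, item 1, lists four point estimates for the unaided and aided reads: "Cut points will be used to establish point based estimates, namely; Sensitivity, Specificity, PPV and NPV". Section 3.1 names the source: the readers' follow-up recommendations "will be used to calculate sensitivity and specificity, PPV and NPV".

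The case set is also described in Section 3.1. "Retrospective lung CT image series from approximately 300 patients will be included in the study". On the cancer group the section says: "Approximately one hundred (100) of the patients will have pathology confirmed cancers". The remaining 200 or so are normals. Enrichment is explicit: "The selected sample, randomly selected from a larger pool of CT cases will be enriched in the following way". The listed steps restrict cancers to 20 mm or less and add non-solid nodules. For the non-solid group the plan adds: "For this group, to have sufficient cases, we may have to include benign (non-malignant) non-solid nodules". Prior scans on which a nodule was visible but not acted on also count as nodule images. No numbers are given for the benign non-solid cases or the prior scans.

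No section gives an intended-use prevalence, a reweighting of PPV and NPV, or a statement on how far they may be generalised. Each radiologist reads the same images in both sessions (Section 3.1). The hypotheses in Section 3.2 concern the LROC AUC and reading time; none concerns PPV or NPV.

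**The concern.** Sensitivity is computed within the cancers and specificity within the normals, so the ratio of cancers to normals does not enter either. PPV and NPV combine the two groups, so that ratio enters both. Here the sponsor chose the ratio; it was not observed in a clinical population. The plan lists the four measures together as if they could be read in the same way.

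A reader who takes the reported PPV or NPV at face value would carry over a number determined largely by the 1:2 sampling. The same applies to a reported gain in NPV: in absolute terms it could be many times what a user would see where cancer is much rarer. The composition is also not fully settled, because the plan does not say whether benign non-solid cases count as positive or negative, and that choice changes the denominators.

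**Working it through.** The plan states no PPV, NPV, reader sensitivity or specificity, or target prevalence, so there is no figure of its own to reproduce.

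**Inputs**
- Study prevalence p = 100/(100 + 200) = 0.333, from Section 3.1.
- Sensitivity (Se) and specificity (Sp): not in the documents. Assumed 0.80 and 0.80 for the main illustration. Six pairs were tried for the range: Se/Sp of 0.60/0.85, 0.70/0.85, 0.70/0.80, 0.80/0.80, 0.60/0.90 and 0.70/0.90.
- Comparison prevalences of 5% and 1%: assumed.
- Sensitivity difference of 0.0914: from Section 3.3, used only as an illustration.

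**Formulas**
- PPV = Se·p / [Se·p + (1 − Sp)(1 − p)]
- NPV = Sp(1 − p) / [Sp(1 − p) + (1 − Se)p]

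**Step 1: same reading performance, different prevalence (Se = Sp = 0.80)**

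| p | PPV | NPV |
|---|---|---|
| 1/3 | 0.2667/(0.2667 + 0.1333) = 0.667 | 0.5333/(0.5333 + 0.0667) = 0.889 |
| 0.05 | 0.040/(0.040 + 0.190) = 0.174 | 0.760/(0.760 + 0.010) = 0.987 |
| 0.01 | 0.008/(0.008 + 0.198) = 0.039 | 0.792/(0.792 + 0.002) = 0.9975 |

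Over the six assumed pairs, PPV is 0.64 to 0.78 at 33% and 0.03 to 0.07 at 1%. NPV is 0.81 to 0.89 at 33% and above 0.995 at 1%.

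**Step 2: effect of the sponsor's choice of mix alone (Se 0.70, Sp 0.85)**
- 100 cancers, 200 normals (33.3%): PPV = 0.700.
- 110 and 190 (36.7%): PPV = 0.730.
- 120 and 180 (40%): PPV = 0.28/(0.28 + 0.09) = 0.757.

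PPV rises by nearly 6 points with no change in how any case is read.

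**Step 3: size of an aided-unaided difference**

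Two assumed scenarios. In A, Se rises from 0.80 to 0.90 while Sp falls from 0.80 to 0.75. In B, Se rises from 0.60 by 0.0914 to 0.6914, with Sp fixed at 0.85.

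| Scenario | p | PPV unaided → aided | NPV unaided → aided | NPV change, points |
|---|---|---|---|---|
| A | 1/3 | 0.667 → 0.643 | 0.889 → 0.9375 | 4.9 |
| A | 0.01 | 0.039 → 0.035 | 0.9975 → 0.9987 | 0.1 |
| B | 1/3 | 0.667 → 0.697 | 0.810 → 0.846 | 3.7 |
| B | 0.01 | 0.039 → 0.044 | 0.9953 → 0.9963 | 0.1 |

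**Step 4: direction of the difference**

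In odds form, PPV/(1 − PPV) = LR+ × p/(1 − p) and (1 − NPV)/NPV = LR− × p/(1 − p), where LR+ = Se/(1 − Sp) and LR− = (1 − Se)/Sp. At a prevalence common to both reads, PPV is therefore ordered by LR+ and NPV by LR−, whatever p is. This holds for each reader, or for sensitivity and specificity pooled over readers.

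In scenario A, LR+ goes from 0.80/0.20 = 4.0 to 0.90/0.25 = 3.6, and LR− from 0.20/0.80 = 0.25 to 0.10/0.75 = 0.133. PPV falls and NPV rises at both prevalences, as the table shows. Prevalence changes the size of the differences and leaves their sign alone.

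**The case against.** The strongest reply is that these are paired descriptive measures and nothing inferential rests on them. Section 2.0 compares scores and actions with the true status of the study case; it does not say that PPV and NPV estimate clinical predictive value. Both reads use the same images, so a difference between them cannot come from the case mix. Sensitivity and specificity are reported alongside, so anyone can derive predictive values at a prevalence of interest. All of this stands. It limits the point to the level and absolute size of PPV and NPV. It does not remove it, because both are named endpoints and the plan attaches no caveat.

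The NPV illustration also depends on the scale. In scenario A, 1 − NPV falls from 0.111 to 0.0625 at 33% (a 44% relative reduction) and from 0.00252 to 0.00134 at 1% (about 47%). The relative effect is nearly stable and only the absolute difference shrinks. That is correct, and is why the point concerns absolute differences.

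Finally, Bayes' rule does not make the results fully transportable. The set is also enriched by spectrum (nodules of 20 mm or less, added non-solid nodules, prior scans), so the estimated sensitivity and specificity are themselves specific to it. This stands and belongs in the fix.

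A reader might infer that PPV and NPV here reflect the case mix and not the reading, or that the aided-unaided comparison is an artefact. The documents do not support either: PPV and NPV also depend on sensitivity and specificity, and the mix is identical in both reads.

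**Conclusion.** The point holds for absolute values and absolute differences. Followed as written, the plan yields PPV and NPV tied to a prevalence of about 33% that was set by sampling. With Se = Sp = 0.80, the same reading gives a PPV of 0.67 in the study set, 0.17 at 5% and 0.04 at 1%. An NPV gain of 4 to 5 points in the study set can correspond to about 0.1 point at 1%.

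The 33% comes from the plan. The sensitivities, specificities and lower prevalences are assumptions. That no adjustment will be made is inferred from the plan's silence; no section says so outright.

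It might be inferred that the reported PPV will be far too high, or that these endpoints can answer no useful question. Neither follows. The documents give no intended-use prevalence, so the PPV overstates clinical use only if that prevalence is below 33%, and far so only if it is well below. As paired descriptors within the study the measures remain valid in direction. The primary LROC AUC conclusion and the reading-time test are unaffected.

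**What to change.** Amend Sections 2.0 and 3.1, and add a short analysis paragraph to Section 3.2:

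1. Report positive and negative likelihood ratios for each read, or PPV and NPV restated by Bayes' rule from each read's estimated sensitivity and specificity over a stated range of prevalence that includes the intended-use setting.
2. Obtain confidence intervals by resampling readers and cases together, with cancers and normals resampled separately. Section 3.2 already allows a multi-reader multi-case bootstrap for the AUC, which could be extended to these measures.
3. If raw PPV and NPV are kept, label them as specific to a set with about one-third cancer.
4. State that the restated values correct for prevalence only, not for the enriched spectrum of nodules and prior scans.
5. State whether benign non-solid cases count as positive or negative in these calculations, and how prior scans enter the denominators.

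The cost is SAP wording and a short calculation on data already to be collected; no cases, readers or sessions are added. The sponsor must state and defend an assumed prevalence range, and the reported PPV will be lower if intended-use prevalence is below 33%.

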3.0 STUDY DESIGN

3.1 OVERVIEW

A reader study with at least ten (10) participating radiologists will be conducted. A localized receiver operating characteristic curve will be used to evaluate radiologists' diagnostic performance (in terms of the trade-off between the sensitivity and specificity when the decision criteria changes) in the detection of lung nodules on lung CTs with and without the

usage of the *ClearRead CT Insight* system. The time needed for the review and interpretation of each case will also be recorded.

An initial (baseline) interpretation will be made by each of the radiologists based on the Lung CT in its original form. At a minimum of one month later, each radiologists will again interpret the same images viewing the pair of CRCTI CT series: Two sets of CT images (standard with CADe marks and processed with vessel suppression) will be presented on either one large monitor or two adjacent monitors.

During the baseline reading the radiologist will mark the location of the actionable nodules and assign a score. The radiologist will also indicate the recommended method of follow-up (Contrast CT, PET-CT, CT Follow-up, Biopsy).

During the second reading session (concurrent read), the radiologist will be presented with a standard appearing CT with CADe marks placed (left image) and the vessel suppressed same slice with the vessel suppressed view (right image). The second image, vessel suppressed, will be grayed out until the radiologist move the mouse to the second panel. The radiologist will mark locations. These may or may not correspond to the locations of the CAD markers. As before, the radiologist will assign a level of suspicious to each mark and indicate the need, if any, of an additional diagnostic action (Contrast CT, PET-CT, CT Follow-up, or Biopsy).

[figure not shown]
Based on the levels of suspicion for each nodule and the associated likelihood ratings, LROC curves will be constructed for both the baseline and the concurrent reads and the significance of any difference will be calculated. The recommendations for further action (Contrast CT, PET-CT, CT Follow-up, or Biopsy) will be used to calculate sensitivity and specificity, PPV and NPV.

Number and types of cases:

Retrospective lung CT image series from approximately 300 patients will be included in the study. Approximately one hundred (100) of the patients will have pathology confirmed cancers and approximately two hundred (200) of the patients will be CTs associated with normal patients. Also included as nodule images are those where the actionable nodule was not acted on at that time, but was detected and acted on based on a subsequent CT. These are the prior images where the nodule can be identified and its location is the same as on the “current” image confirmed by the radiologist expert panel (using a majority of three as the decision criterion).

The selected sample, randomly selected from a larger pool of CT cases will be enriched in the following way:

1. Lung nodules (cancers in this study) will be tumor size T1a (20 mm or less). The proportion of nodules 20 mm or less may be increased since this is where we expect the major impact of this software to be.
2. Non-Solid (ground glass) nodules will be added to the sample (based on availability) to determine the performance of the system on non-solid nodules. For this group, to have sufficient cases, we may have to include benign (non-malignant) non-solid nodules.
3. In this project, VIRGINIA TECH will perform a Machine Test of the ClearRead-CT-Insight algorithm followed by a reader performance evaluation study. Riverain will provide a system configured with the operating point set to be used for the reader studies and a configuration for an “open” system to be used for machine testing and FROC generation. Figure 1 shows the reader performance study consists of two arms; **Arm 1**: a baseline read (no secondary content) and **Arm 2**: concurrent, CAD augmented read.

1/12/2015

Riverain Technologies, LLC - Confidential

Figure 1: ClearRead Insight Reader Study Design

1st Arm: Do baseline (measure time, readers score regions according to action and suspiciousness) – mark all locations of concern

2nd Arm: Concurrent read (measure time, readers score regions according to action and suspiciousness) – mark all locations of concern

The primary study hypothesis is that the adjunctive use of ClearRead CT Insight is superior to use of standard lung CT images alone, as measured by the area under the LROC curve.

3.2 STATISTICAL ANALYSES

Accuracy

To evaluate the hypothesis of superiority in terms of improvement in accuracy for ClearRead CT Insight vs. unaided, a mixed effects model (DBM) will be implemented (similar to the model outlined in Dorfman, Berbaum and Metz, 1997), where variance components will be included to account for reader, case, reader by case, reader by modality, case by modality and reader by case by modality. However, it is anticipated that the three-way interaction will be inestimable and will subsequently be dropped from the statistical model. Specifically, the hypothesis to test for superiority of ClearRead CT Insight vs. unaided is:

$$H_0: AUC_{\text{unaided}} - AUC_{\text{ClearRead CT Insight}} \geq 0.0 \text{ vs. } H_A: AUC_{\text{unaided}} - AUC_{\text{ClearRead CT Insight}} < 0$$

The AUC of the LROC is the primary endpoint to evaluate accuracy and the test of interest will be a two-sided 95% confidence interval on the effect of modality (i.e. *ClearRead CT Insight minus unaided*). Significance will be concluded if the upper bound of the two-sided 95% confidence interval does not include zero. If the null hypothesis (H_0) is rejected, the alternative hypothesis (H_A) is accepted and the superiority of using the ClearRead CT Insight system will be established.

Time

The second co-primary objective is to evaluate reduction in time spent per image for *ClearRead CT Insight vs. unaided*. Specifically, the hypothesis to test for superiority of *ClearRead CT Insight vs. unaided* is:

$$\mathbf{H_0 = T_{unaided} - T_{ClearRead CT Insight} \leq 0 \text{ vs. } \mathbf{H_A = T_{unaided} - T_{ClearRead CT Insight} > 0}$$

To evaluate the hypothesis of non-inferiority in terms of improved read time for *ClearRead CT Insight vs. unaided*, a mixed effects model will be implemented (similar to the model outlined in Dorfman, Berbaum and Metz, 1992), where variance components will be included to account for reader, case, reader by case, reader by modality, case by modality and reader by case by modality. However, it is anticipated that the three-way interaction will be inestimable and will subsequently be dropped from the statistical model.

The read times will be tested using a two-sided 95% confidence interval on the effect of modality (i.e. *ClearRead minus unaided*). Significance will be concluded if the upper bound of the two-sided 95% confidence interval does not include zero.

With either analysis, the use of the mixed model could be modified to employ a bootstrap sampling approach if the model assumptions of the DBM method have been violated. The upper 95 % confidence limit for the difference in the areas under the curves would be calculated using 10,000 bootstraps in the MultiReader MultiCase (MRMC) ROC method.

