Table VI presents a summary of the power simulations along with additional scenarios with fewer cases with 8 or 10 readers. Superiority is assessed as the proportion of simulations in which the upper bound of the confidence interval on the AUC difference is less than zero. The other power assessment is on the statistical significance of the difference between modality.

Table VI: Power estimates for superiority and statistically significant modality effect using previous Softview reader study to estimate variance components

			Power	
Number of Cases	Number of Readers	Effect Size	Superiority	Modality Effect
300	10	0	0.086	0.082
		0.05	0.606	0.490
		0.1	0.978	0.974
		0.2	1.0	1.0
		0.5	1.0	1.0
270	10	0	0.060	0.060
		0.2	1.0	1.0
		0.5	1.0	1.0
270	8	0	0.058	0.080
		0.1	0.932	0.878
		0.2	1.0	1.0
		0.5	1.0	1.0

The results show that the type I error is approximately controlled at the nominal level, i.e. 0.05, and therefore type I error is maintained at the desired level. Furthermore, the power to detect a change in AUC of at least 10% of the standard deviation is over 80% given the assumed magnitude of the variance components, even with only 270 cases and 8 readers.

Based on data from the literature referenced earlier in this report, potential variability and effect size for sensitivity can be assessed. Based on a mean difference in sensitivity of 0.0914 with overall standard deviation over all estimates of 0.1234 for an effect size of $0.0914/0.1234$, or 0.741, the superiority of ClearRead CT Insight would be detected with adequate power.

There are several scenarios including reduced number of cases and a reduced number of readers. Even with 270 cases and only 8 readers, the power of the study should be sufficient to detect an effect size of 0.1.

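### The AUC success rule puts the upper bound on the wrong contrast: read literally, it can declare ClearRead superior only when the observed aided AUC is lower

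*Combined protocol and SAP*

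**What the plan says.** All references are to the combined protocol and SAP.

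- **Hypotheses (Section 3.2, Accuracy).** H0 and H_A are written on AUC(unaided) minus AUC(ClearRead). H_A is that this difference is below zero, meaning that the aided read is better.
- **Interval (same subsection).** The plan says that "the test of interest will be a two-sided 95% confidence interval on the effect of modality", and defines that effect as "ClearRead CT Insight minus unaided". This is the opposite sign to the hypotheses.
- **Decision rule (same subsection).** "Significance will be concluded if the upper bound of the two-sided 95% confidence interval does not include zero". If H0 is rejected, "the superiority of using the ClearRead CT Insight system will be established".
- **Bootstrap fallback (end of Section 3.2).** "The upper 95 % confidence limit for the difference in the areas under the curves would be calculated using 10,000 bootstraps". The direction of subtraction is not given.
- **Power (Section 3.3, text introducing Table VI).** "Superiority is assessed as the proportion of simulations in which the upper bound of the confidence interval on the AUC difference is less than zero". Again, the sign of the difference is not given.
- **Reading time (Section 3.2, Time).** The same interval contrast and the same decision sentence are used.

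**The concern.** A larger AUC is better, so on ClearRead minus unaided a benefit is positive, and superiority needs the lower bound to lie above zero. The plan looks at the upper bound instead. For reading time the same sentence has the right direction, because a shorter aided read makes ClearRead minus unaided negative. For AUC it is reversed.

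This is the pre-specified success criterion for the primary endpoint. Taken literally, a device that improves AUC fails it and a device that lowers AUC can pass it. If the sign or the bound is chosen only when the data are analysed, the criterion was not pre-specified.

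**Working it through.** **1. The algebra, which needs no variance assumption.** Let d be the observed ClearRead minus unaided difference in AUC and SE its standard error.

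- Upper bound below zero: d + 1.96·SE < 0, that is d < −1.96·SE. This requires d to be negative.
- Lower bound above zero: d − 1.96·SE > 0, that is d > 1.96·SE. This is the intended test, and it is the same as an upper bound below zero on unaided minus ClearRead.

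**2. Inputs (Section 3.3).** 300 cases and 10 readers. Scaled variance components from Table V: modality-by-reader 3.8981E-05, modality-by-case 0.0257, residual 0.8355. The reader, case and reader-by-case components cancel in the difference between modalities. The mean difference is the effect size times the residual standard deviation.

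**3. Standard error (normal approximation to the mixed model).**

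SE = √[2 × (0.000038981/10 + 0.0257/300 + 0.8355/3000)] = 0.0271

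**4. Mean difference at effect size 0.1.** 0.1 × √0.8355 = 0.0914. Section 3.3 prints 0.084 for this product, which is 0.1 × 0.8355 without the square root. That is a separate slip, and 0.0914 follows the plan's own formula.

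**5. The plan's own figure.** Table VI gives superiority power of 0.978 for this design at effect size 0.1. The approximation gives:

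| Treatment of modality-by-case | Two-sided 95% interval | One-sided 0.05 |
|---|---|---|
| Included throughout (SE 0.0271) | 0.921 | 0.958 |
| Omitted throughout (SE 0.0238) | 0.970 | 0.986 |
| In the data, omitted from the test's SE | 0.951 | 0.973 |

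The full Table V model therefore does not reproduce 0.978. The last variant at one-sided 0.05 comes within 2 percentage points of every superiority figure in Table VI that is below 1.0. Every variant counts success in the direction where the aided read is better. Under the literal rule, power at this effect size would be close to zero.

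**6. Probability of success under each rule (SE 0.0271, 95% interval).** For a true difference δ, the written rule succeeds with probability Φ(−1.96 − δ/SE) and the intended rule with probability Φ(δ/SE − 1.96). At effect size 0.1, δ/SE = 0.0914/0.02713 = 3.369. This gives Φ(−5.329) = 4.9 × 10⁻⁸ and Φ(1.409) = 0.921.

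| True effect size (aided minus unaided) | Written rule: upper bound < 0 | Intended rule: lower bound > 0 |
|---|---|---|
| +0.1 | 0.00000005 | 0.921 |
| +0.05 | 0.00013 | 0.391 |
| 0 | 0.025 | 0.025 |
| −0.05 | 0.391 | 0.0001 |
| −0.1 | 0.921 | effectively 0 |

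With modality-by-case omitted (SE 0.0238), the +0.1 row becomes 3 × 10⁻⁹ and 0.970, and the +0.05 row becomes 0.00005 and 0.485.

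**7. A single result.** Suppose the observed benefit is 0.0914 with SE 0.0271. The interval for ClearRead minus unaided is 0.0914 ± 1.96 × 0.0271 = (0.038, 0.145). The aided read is clearly better, but the upper bound is above zero and the written rule fails. On unaided minus ClearRead the interval is (−0.145, −0.038), the upper bound is below zero, and H0 is rejected as intended.

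**The case against.** The strongest reply is that the intent is plain. The study objective, the hypothesis at the end of Section 3.1 and H0/H_A all point the right way, and superiority is tied to rejecting an H0 that contains every worse aided AUC. The upper-bound rule and Section 3.3 both agree with H_A if the difference is unaided minus ClearRead. On this view only the parenthetical naming the contrast is out of line, and the realistic risk is ambiguity, not a harmful device being declared superior. This stands as a description of where the fault lies. It does not remove the fault, because the parenthetical names the contrast on which the primary test is decided and no other text overrides it.

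A second reply is that the sentence is loose. A bound is one number and cannot include zero, so the authors may have meant that the interval excludes zero. The words do say upper bound, however, and Section 3.3 reads the rule as upper bound below zero. An interval that merely excludes zero has no direction, so a significantly worse aided read would pass too, contrary to the one-sided H_A. If the phrase means only that the upper bound is not equal to zero, almost any result passes. None of these literal readings gives the intended test.

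Two limits are fair. The bootstrap paragraph and Section 3.3 state no sign, so on their own they are ambiguous and not wrong. Also, worse here means observed worse: with no true difference, the literal rule still succeeds 2.5% of the time.

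**Conclusion.** The concern holds. On the contrast that the plan names for its primary interval, the success rule runs in the wrong direction and contradicts the plan's own alternative hypothesis. The conclusion needs only two things: that the contrast is ClearRead minus unaided, as Section 3.2 states, and that the rule means an upper bound below zero, as Section 3.3 states.

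The probabilities (about 5 × 10⁻⁸ against 0.92 at effect size 0.1, and 0.0001 against 0.39 at 0.05) rest additionally on Table V and a normal approximation. They illustrate the size of the error, and the shortfall from Table VI's 0.978 has no bearing on its sign. Because this is the primary decision rule, it must be corrected before the analysis.

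**What to change.** In Section 3.2 (Accuracy), replace the decision sentence with: *Superiority is concluded if the lower limit of the two-sided 95% interval for AUC(ClearRead CT Insight) minus AUC(unaided) is greater than zero.* Then:

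- restate H0 and H_A on that contrast (H0: difference ≤ 0; H_A: difference > 0);
- in the bootstrap paragraph, name the contrast and use the lower limit. For a percentile interval this is the 2.5th percentile, which matches the stated two-sided 95% level;
- in Section 3.3, describe superiority as the lower bound above zero on the same contrast.

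An equivalent and shorter edit defines the interval as unaided minus ClearRead and requires the upper bound to be below zero, with that contrast named in the bootstrap paragraph and in Section 3.3. Either is acceptable, provided that one contrast, one bound and one confidence level are used throughout.

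The reading-time rule keeps its upper bound, but its wording should also say that the bound is below zero. The cost is wording only, with no change to cases, readers or data collection.
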